Quantitative observational comparative effectiveness of quadratus lumborum block with liposomal bupivacaine (Exparel®) versus thoracic epidural analgesia in patients undergoing laparoscopic colectomy

NCT03827291

Document Date: 09/27/2022

Purpose of the Study

We believe that a quadratus lumborum block with liposomal bupivacaine(Exparel®) or a quadratus lumborum block with an admixture of bupivacaine will provide roughly equivalent analgesia and opioid use when compared with postoperative analgesia in a historical cohort that received thoracic epidural analgesia. We believe participants who receive the quadratus lumborum block will result in improved early mobilization, fewer complications such as block failure, urinary retention, and pruritis, and decreased overall pharmacy costs compared to the patients who received thoracic epidural analgesia.

Background & Significance

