Laparoscopic colectomy is a surgical procedure that is primarily performed for resection of a GI malignancy. While most of the procedure is performed via laparoscopic ports in the anterior abdominal wall, the resected specimen is typically delivered through a small lower abdominal laparotomy, which results in a moderately severe burden of pain for these patients. Enhanced recovery after surgery (ERAS) protocols are aimed at improved return to function with minimal disruption in the functional capacity, and have been shown to reduce hospital length of stay, complications, and costs. One standard therapeutic component of the ERAS program at Duke for colorectal surgery is thoracic epidural analgesia (TEA), which is typically maintained for 2 days postoperatively. While TEA usually provides high-quality analgesia of the abdomen, drawbacks include technical difficulties with insertion, patchy or non-functioning block, pruritis and/or urinary retention due to epidural opioids, impairment of mobility due to leg weakness or the presence of a pump apparatus on an IV pole, and most importantly, associated hypotension which often results in the epidural local anesthetic infusion being discontinued. Alternatives to TEA include infiltrative blocks of the wall of the abdomen. The quadratus lumborum block (QLB) is a novel, ultrasound-guided infiltration technique whereby local anesthetic is deposited in the fascial plane between the quadratus lumborum and psoas major muscles at the level of L3-4.(1) Performed bilaterally, the QLB has been shown to provide a dermatomal block of the entire anterior abdominal wall. This may be the principal advantage of QLB over transversus abdominis plane (TAP) block, which is often patchy and restricted to a smaller area of the abdominal wall. In our institution, QLB is replacing TAP blockade for many abdominal procedures that have both upper and lower incisions or port sites. The QLB appears (both in the scant literature to date and in our institutional experience) to be reliable and technically simpler to perform than TAP blocks, as the needle is not moved once the fascial plane is breached. We wish to compare the effectiveness of QL blocks for postoperative analgesia in this population with a historical cohort that received thoracic epidural analgesia. Based on our experience, we believe that infiltrating this space with an admixture of bupivacaine and liposomal bupivacaine will result in excellent pain relief for an extended duration of time. Liposomal bupivacaine (Exparel®) is a slow-release, long-acting form of bupivacaine that has been shown to provide extended duration of analgesia and opioid sparing

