Following the block, subjects will proceed to the operating room where they will undergo a standard general anesthetic with endotracheal intubation (desflurane or isoflurane in a mixture of air/oxygen). The dosing of intraoperative opioids will be left to the discretion of the attending anesthesiologist in the room.

In the Post-Anesthesia Care Unit (PACU) and on the postoperative floor, subjects will have access to oxycodone 5-15 mg PO q3h prn for rescue analgesia (the primary outcome measure). In the PACU, patients will also have access to intravenous hydromorphone if the oral opioid

provides inadequate relief. Finally, subjects may receive a standard multimodal analgesia regimen consisting of:

- Acetaminophen 975 mg PO q6h (beginning in preop holding)
- Gabapentin 600 mg PO once in holding, then 100 mg PO tid thereafter
- Ketorolac 15 mg IV prior to skin closure

While this standard regimen is expected, it may vary per clinical care team judgement and/or preference. Any alterations in this standard regimen will not be considered a protocol deviation.

Assessments

Patient assessments will be performed or recorded by a research assistant twice daily (unless otherwise specified). Assessments made after discharge will be recorded by subjects who will be provided with a diary to document the outcomes. Outcomes to be measured include:

Opioid consumption. Cumulative opioid consumption over 48 hours is the primary outcome measure. Data will be drawn from PACU records and from the nursing medication records on a twice-daily basis. Post discharge opioid use will be tracked in the take-home patient diary. The patient will be called at 7 days after surgery to collect.

NRS-11. The 11-point Numeric Rating Scale (0-10) will be used as a secondary outcome measure. Two measures will be taken with each assessment, one at rest and one with coughing. These will be conducted preoperatively, 30 minutes after arrival to PACU, and at time points 8 hrs., 24 hrs., 36 hrs. 48 hrs, 72 hrs, 96 hrs., 120 hrs., 144 hrs. and 168 hrs.

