- Patients scheduled for elective, laparoscopic colonic resection by one of three surgeons: Drs. [name], [name] or [name]. These surgeons perform this procedure in the same manner
- Age 18-85 years
- American Society of Anesthesiologists (ASA) Physical Class I-III
- BMI 18-35 kg/m²

Criteria for exclusion in Prospective Cohort:

- Inability to consent
- Inability to speak English
- Pregnancy
- Emergency surgery
- Contraindications to regional blockade: coagulopathy or bleeding diathesis, local infection, allergy to local anesthetics
- Allergies/intolerances/contraindications to any of the multimodal agents (acetaminophen, gabapentin, ketorolac)
- Daily opioid equivalent use of 30 mg of morphine or greater at time of consent
- History of drug or alcohol abuse
- Uncontrolled anxiety, schizophrenia or other psychiatric disorder that, in the opinion of the investigator, may interfere with the study assessments of compliance.

Criteria for inclusion in Retrospective cohort:

- Patients that have had a laparoscopic colonic resection in the past year by Drs. [name], [name] or [name] and received thoracic epidural analgesia.
- Thoracic epidural analgesia must be placed in preoperatively, must be sited between levels T8 and T12, and must be started while the case is going- i.e. not started in PACU.
- Age 18- 85 at the time of the procedure.
- American Society fo Anesthesiologists (ASA) Physical class between I- III.
- BMI 18- 35 kg/m².

- Received the standard multimodal medication regimen for pain as outlined in the ERAS protocol for colorectal surgery

Criteria for exclusion in Retrospective cohort:

- Emergency surgery
- Daily opioid equivalent use of 30 mg of morphine or greater at time of consent.
- History of drug or alcohol abuse.
- Uncontrolled anxiety, schizophrenia or other psychiatric disorder.

Risk/Benefit Assessment

Risks of the study intervention relate to those associated with the quadratus lumborum block. These include routine risks of block procedures including bleeding, infection, nerve damage, local anesthetic systemic toxicity, as well as transient weakness of the hip flexor muscles (a known possible side-effect of QL block).

If subjects receive the quadratus lumborum block, they may experience improved pain control and/or reduced side effects compared to the epidural pain relief option, but it is not known yet whether this will be the case.

Data Analysis & Statistical Considerations

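### The entry rules for the epidural cohort remove abandoned and never-started epidurals, so the block-failure comparison covers only delivered epidurals and is biased against QLB on that outcome

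*Combined protocol and SAP*

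**What the plan says.** The Purpose of the Study predicts that QLB will give "fewer complications such as block failure, urinary retention, and pruritis" compared with TEA. For TEA, the Background & Significance section says that "drawbacks include technical difficulties with insertion, patchy or non-functioning block" are among the problems.

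Under Selection of Subjects, the retrospective cohort takes patients who had the operation in the past year "and received thoracic epidural analgesia". The next criterion requires preoperative placement and adds that the epidural "must be sited between levels T8 and T12, and must be started while the case is going", so a start in PACU does not qualify. These conditions describe how the treatment was delivered. The prospective cohort is defined before treatment: "Patients scheduled for elective, laparoscopic colonic resection by one of three surgeons", with limits on age, ASA class and BMI. None of its criteria concerns whether the QLB was completed or worked.

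Block success is an outcome in both cohorts. The Assessments section tests QLB by pinprick in four abdominal quadrants. It takes epidural success or failure from the anesthesia record and pain-service notes, at 30 minutes in PACU and at 8, 24, 36, 48 and 72 hours. Data Analysis & Statistical Considerations plans Wilcoxon rank sum or Fisher exact tests. It defines no analysis set and gives no rule for an incomplete QLB.

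**The concern.** A failure rate needs a denominator that includes the attempts that failed. Here one cohort is selected on treatment delivered and the other on surgery scheduled. An insertion that was attempted and abandoned, or an epidural that was never started, is a plain failure of the technique, and the Background itself names insertion difficulty. Those patients are screened out before the rates are compared.

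The recorded TEA failure rate would then be lower than the rate among patients in whom an epidural was attempted. A result of no fewer failures with QLB could come partly from the entry rules, and a real QLB advantage on a stated hypothesis could be hidden.

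**Working it through.** **The plan's own figure.** The only sample size is for 48-hour opioid use. Inputs from Sample Size Justification: mean 20 mg, SD 5.2 mg, margin 20% of 20 mg = 4 mg, alpha 0.05, power 0.80. Per group, n = 2 × (1.960 + 0.842)² × 5.2² / 4² = 26.5, so 27 per group and 54 in total, as stated. This takes 0.05 as two-sided; one-sided 0.05 gives 21 per group. The present point does not change this figure. Block failure has no sample size of its own.

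**Which events can be counted, as written**

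| Event | TEA cohort | QLB cohort |
|---|---|---|
| Attempted and abandoned | Not admitted | Not excluded by any criterion; no scoring rule |
| Epidural never started | Not admitted | Not applicable |
| Epidural outside T8-T12 | Not admitted, whether or not it worked | No level criterion |
| Epidural first started in PACU | Not admitted, whether or not it worked | Not applicable |
| Delivered, then patchy, non-functioning or (for TEA) stopped | Admitted and recorded | Admitted and tested by pinprick |

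**Size.** The documents give no failure rates, so every rate below is an assumption. Let e be the share of attempted epidurals removed by the entry rules, w the share of those that were failures, and r the failure rate among epidurals admitted.

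- True rate = e × w + (1 − e) × r. Observed rate = r. Difference = e × (w − r).
- All removed epidurals failed (w = 1), r = 10%, e = 5%: 0.05 + 0.95 × 0.10 = 14.5%.
- Same with e = 15%: 0.15 + 0.85 × 0.10 = 23.5%.
- In 30 patients: 0.145 × 30 = 4.4 and 0.235 × 30 = 7.1 failures, against 0.10 × 30 = 3.0 observed.
- Only half of those removed failed (w = 0.5): 0.05 × 0.5 + 0.95 × 0.10 = 12.0% and 0.15 × 0.5 + 0.85 × 0.10 = 16.0%.
- If removed epidurals failed no more often than the rest (w = r), the difference is zero.

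For abandoned and never-started epidurals w is 1 by definition, so for them the direction is settled. For off-level or PACU-started epidurals w is unknown.

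**Effect on the test.** Assume 20% true TEA failure, 5% QLB failure, and half of TEA failures removed. Observed TEA failure is 0.20 × 0.5 / (1 − 0.20 × 0.5) = 11.1%, and the risk difference falls from 15 to 6.1 points. Exact Fisher power (two-sided 0.05) falls from 0.44 to 0.11 with 30 TEA and 45 QLB patients, reading the planned 45 as all QLB. With 27 QLB patients it falls from 0.26 to 0.03.

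**The case against.** **The cohort is not restricted to working epidurals.** A reader might infer that failed epidurals as a class are removed and that the objective cannot be answered. The documents do not support this. The criteria cover receipt, timing, level and start, not function, and later failures are recorded up to 72 hours. The objective is narrowed, not lost.

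**Off-level or late-started is not the same as failed.** A reader might score every excluded epidural as a failure. No section does so, and either kind could have worked well. Counting them automatically would tilt the comparison towards QLB.

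**The bias is not shown on every outcome.** A reader might extend it to mobilisation. The Background attributes impaired mobility to leg weakness and the pump, and pruritus and urinary retention to epidural opioids. A patient whose insertion was abandoned would have none of these, so requiring a delivered epidural could make TEA look worse there.

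**The strict cohort is defensible for the primary.** In a non-inferiority comparison of opioid use, a well-delivered comparator is the conservative choice for QLB. If half of TEA failures were removed, with true failure of 10-30% and 5-20 mg extra opioid per failure (all assumed), the TEA mean would fall by 0.2-2.5 mg against the 4 mg margin. That makes non-inferiority harder to show. This stands, and the primary cohort should stay.

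**That every QLB patient counts is only an inference.** It rests on the absence of a rule, and contraindications to regional blockade are excluded prospectively. This too stands; the missing rule is part of what needs fixing.

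**Other differences remain.** Failure is measured by pinprick in one cohort and from chart notes in the other. The TEA criteria also require that patients "Received the standard multimodal medication regimen for pain as outlined in the ERAS protocol for colorectal surgery", whereas for QLB "Any alterations in this standard regimen will not be considered a protocol deviation". Widening the denominator cures neither. Block failure is also secondary, and power is modest even without selection. These limit what the fix achieves, but do not justify leaving abandoned insertions out of a failure rate.

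**Conclusion.** The point holds for block failure. Abandoned and never-started epidurals cannot be counted as TEA failures, no parallel condition applies to QLB, and the resulting bias on this outcome runs against QLB: it can hide an advantage but does not create one.

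Its size cannot be computed from the documents. Under the assumed rates the understatement is 4.5 to 13.5 percentage points (14.5 − 10 and 23.5 − 10), or roughly 1 to 4 patients in 30. Those figures treat every removed epidural as a failure and shrink if some worked.

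The plan should be changed here, but the point touches a secondary outcome. It does not undermine the opioid primary or its sample size.

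**What to change.** 1. Keep the strict TEA cohort for the 48-hour opioid primary.
2. For block failure, use as the TEA denominator all otherwise eligible patients of the three surgeons in the same period in whom a preoperative thoracic epidural was attempted. The receipt criterion and the placement, level and start criterion would both be set aside for this outcome only.
3. Count abandoned insertions and never-started epidurals as failures. Classify off-level or PACU-started epidurals by the success or failure recorded in the anesthesia and pain-service notes, not automatically as failures.
4. Use all attempted QLBs as the QLB denominator, and count an incomplete QLB as a failure.
5. Report the number of TEA patients excluded by each criterion.

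The cost is a wider search of record types already under review, which depends on attempts being documented there, and a block-failure denominator that differs from the primary cohort and must be labelled as such. No extra prospective patients are needed.

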
in a number of surgical settings. (2, 3) Liposomal bupivacaine is FDA approved for surgical infiltration, field blocks, fascial plane blocks of the abdomen, dental blocks, and interscalene brachial plexus blocks. A number of new abdominal wall block techniques have been developed over the last several years, and following some initial confusion related to the wording of the label, the FDA issued a clarification letter that stated that truncal fascial plane blocks such as the transversus abdominis plane (TAP) block are an on-label use of the medication (see attached clarification letter). The quadratus lumborum (QL) block is a type of TAP block, wherein local anesthetic is infiltrated into the fascial plane between muscles of the lateral abdominal wall.

Design & Procedures

This is a single center, observational prospective and retrospective cohort study.

Prospective: On the day of surgery, subjects will receive a QLB in the preoperative holding area as follows:

Subjects will be positioned in the right lateral decubitus position, and will be attached to standard ASA monitors (pulse oximetry, EKG, non-invasive blood pressure). Oxygen 5 L/min will be supplied via a face mask. Sedation/analgesia with midazolam 1- 2 mg IV and fentanyl 25- 100 mcg IV will be administered.

After appropriate skin preparation and draping, a 60 mm, 2-5 MHz curvilinear ultrasound transducer will be placed on the skin over the intercristal line (approximately L3/4 disc space) on the midline of the back. The transducer will be translated laterally to the left until the quadratus lumborum and psoas major muscles are identified. The transducer will then be rotated until the quadratus muscle is seen in its long axis, just below its attachment on the 12th rib.

A 21 gauge, 10 cm echogenic block needle (Pajunk Sonoplex, Norcross, GA) will then be inserted from the inferior aspect of the transducer and advanced until the tip is visualized in the fascial plane between the QL and psoas major muscles. Following negative aspiration for blood, 30 ml of injectate will be slowly administered with intermittent aspiration. Each 30 ml aliquot will contain 10 ml of liposomal bupivacaine (133 mg) and 20 ml of 0.25% bupivacaine (50 mg). The block will then be repeated on the right side.

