Historical data of 30 patients that meet inclusion criteria and meet no exclusion criteria, will be collected and for the retrospective group. The anesthesia statisticians will evaluate the following data from the patient's electronic medical record if available, including but not limited to hospital notes, anesthesia notes, medical history, medications, pain service notes, and flowsheets from admission to discharge. Electronic medical records will be used to assess the following items to compare to the prospective cohort.

Opioid consumption. Cumulative opioid consumption at 24hours, 48 hours and 72 hours. 48 hours is the primary outcome measure. Data will be drawn from PACU records and from the nursing medication records.

NRS-11. The 11-point Numeric Rating Scale (0-10) will be used as a secondary outcome measure. These will be collected from the preoperative assessment record, 30 minutes after arrival to PACU, and at time points 8 hrs., 24 hrs., 36 hrs. 48 hrs. and 72 hrs.

Thoracic epidural success and adverse events. Evidence of epidural block success/failure (as described in the anesthesia record and in daily Inpatient Pain Service notes). This will be done at the time of pain assessment (30 minutes after arrival to PACU, and at time points 8 hr, 24 hr, 36 hr and, 48 hr and 72 hr). Subject data will be collected for potential adverse events related to the epidural including evidence of hypotension, urinary retention, inability to ambulate per physical therapy. (known possible side-effect of thoracic epidural approach).

Hospital length of stay. Measured both by raw length of stay and by time to achieving "discharge readiness", defined by the presence of 3 criteria: a pain score of 3 or less with ambulation, no opioids required in the preceding 6 hours, and the ability to perform self-care (go to the toilet, dress, and shower).

Incidence of opioid-related adverse events. Incidence of nausea, vomiting, ileus, constipation, orthostasis, pruritis, urinary retention, respiratory depression

Time to first mobilization. Measured from time of arrival in PACU (time zero)

Cost. Hospital costs including pharmacy-related costs, costs due to opioid-related adverse events, the cost associated with nursing interventions and drugs to treat opioid-related adverse events, and overall hospital admission costs will be calculated.

Selection of Subjects

Criteria for inclusion in Prospective cohort:

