We will use descriptive statistics (mean (SD) or frequency (%)) and group comparisons via Wilcoxon rank sum or fisher exact tests to measure differences between cohorts in opioid consumption, pain scores with rest and activity, and other secondary outcome measures.

Sample Size Justification

A difference in opioid consumption less than 20% would be considered non-inferior. Based on typical postoperative opioid consumption following laparoscopic colectomy (20mg +/- 5.2 mg), a total of 54 subjects (27 in each group) would be required to reject the null hypothesis that QL blockade is inferior in the first 48 hours with the study intervention, given an alpha of 0.05 and a power of 0.8. We plan on recruiting 45 subjects to account for dropout.

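### The non-randomised, non-concurrent comparison of 48-hour opioid use is planned only as crude tests, with no rule for which 30 eligible historical patients are taken

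*Combined protocol and SAP*

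**What the plan says.** Design & Procedures: "This is a single center, observational prospective and retrospective cohort study". The QLB cohort is enrolled prospectively. The TEA cohort is drawn from charts: "Patients that have had a laparoscopic colonic resection in the past year", by the same three surgeons.

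Assessments, retrospective part: "Historical data of 30 patients that meet inclusion criteria and meet no exclusion criteria, will be collected". No sentence says how the 30 are drawn from those who qualify.

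Data Analysis & Statistical Considerations: the cohorts are compared by "descriptive statistics (mean (SD) or frequency (%)) and group comparisons via Wilcoxon rank sum or fisher exact tests". This one sentence is the whole analysis plan. Regression, stratification, matching, weighting and sensitivity analysis for confounding appear nowhere.

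Sample Size Justification: "A difference in opioid consumption less than 20% would be considered non-inferior".

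Selection of Subjects gives criteria for both cohorts. Common to both are the three surgeons, age 18-85, ASA I-III, BMI 18-35, no emergency surgery, daily opioid use below 30 mg morphine, and no drug or alcohol abuse. The lists are not identical:

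- Exclusions for language, contraindication to regional block and intolerance of the multimodal agents are listed only for the prospective cohort.
- The psychiatric exclusion depends on investigator opinion in the prospective cohort and is unqualified for controls.
- Controls must have "Received the standard multimodal medication regimen for pain as outlined in the ERAS protocol for colorectal surgery". For the prospective cohort, "While this standard regimen is expected, it may vary per clinical care team judgement and/or preference".

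The only baseline measure listed for both cohorts is preoperative pain (NRS). Prospectively it is scored at rest and with coughing. For controls, "These will be collected from the preoperative assessment record, 30 minutes after arrival to PACU" and later time points, with no rest or cough distinction.

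**The concern.** Without randomisation, a difference in 48-hour opioid use between the cohorts mixes the effect of the block with any difference in the patients. A crude rank test carries that mixture straight into the primary comparison. Eligibility limits as wide as age 18-85, or any opioid use below 30 mg morphine per day, leave ample room for the cohorts to differ inside them.

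Control selection adds a second route. When the 30 are picked, their opioid totals are already in the record. Without a fixed rule, the choice among eligible patients is open, and a reader cannot tell whether it was made independently of outcome.

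The conclusion at stake is a non-inferiority claim, where a bias towards QLB produces a false positive and a bias away from it hides a true one. The plan gives no means of telling which applies or of correcting either.

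**Working it through.** **Inputs.** From Sample Size Justification: mean 20 mg, SD 5.2 mg (reading the plus-or-minus value as an SD), 20% limit, alpha 0.05, power 0.8, 27 per group. The opioid unit is not stated. Bias sizes and covariate correlations below are assumptions; the documents give none.

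**Step 1: the plan's own figure.** Margin = 0.20 × 20 = 4 mg = 4/5.2 = 0.77 SD. n per group = 2 × [5.2 × (z + 0.842)/4]².

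- One-sided 0.025 (z = 1.960): 26.5, so 27 per group and 54 in total, as stated.
- One-sided 0.05 (z = 1.645): 20.9, so 21 per group, which does not match.

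The sample size therefore implies a test of means against a 4 mg margin at one-sided 0.025. The plan does not name that test. The formula has no term for confounding.

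**Step 2: effect of a net bias in the crude comparison, 27/27.** SE = 5.2 × √(2/27) = 1.415, with 52 df. Non-inferiority is claimed if the upper 95% limit is below 4 mg. By noncentral t, the noncentrality is b/1.415 for a false claim (true difference 4 mg, bias b favouring QLB) and (4 − b)/1.415 for power (true difference 0, bias b against QLB).

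| Assumed bias b | False non-inferiority | Power |
|---|---|---|
| 0 mg | 2.5% | 0.79 |
| 0.5 mg | 5.3% | 0.68 |
| 1 mg | 10.3% | 0.55 |
| 2 mg | 28.3% | 0.28 |

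More patients do not help. At 45/30 (assuming that 45 is the prospective count), a 1 mg bias gives 12.4% false claims.

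**Step 3: what a 1 mg bias requires.** One covariate with correlation r to the outcome, differing by d SD between cohorts, gives a bias of r × d × 5.2 mg. So d = 1/(0.3 × 5.2) = 0.64 SD at r = 0.3, and 1/(0.5 × 5.2) = 0.38 SD at r = 0.5. The chance SD of a standardised difference at 27/27 is √(2/27) = 0.272.

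**Step 4: what adjustment does.** Simulating the r = 0.3, d = 0.64 case at 27/27 with a larger covariate set (8 df), false claims were 10.3% crude and 2.4% adjusted. With the imbalance reversed, power was 0.55 crude and 0.72 adjusted.

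**Step 5: what adjustment costs at 27/27, from 0.79 crude.**

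| Situation | 4 covariate df | 8 covariate df |
|---|---|---|
| Chance imbalance, covariates explain none of the outcome variance | about 0.75 | 0.72 |
| Chance imbalance, covariates explain 20% | about 0.85 | 0.81 |
| One non-prognostic covariate differs by 0.64 SD | about 0.72 | 0.68 |

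**The case against.** **The controls are not chosen freely.** A reader might infer that the plan has no rule for them at all. It has several: a one-year window, three surgeons, an epidural placed preoperatively at T8-T12 and running during the case, limits on age, ASA and BMI, the multimodal regimen, and exclusions. These stand. Some of the listed differences may also matter little in practice, since a control who received an epidural and the multimodal drugs was presumably fit to have them. What is missing is narrower: which 30 of the eligible patients are used.

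**No imbalance is shown.** Correct. A reader might infer that the result will be biased, or biased towards QLB. The documents support neither, and the sign is unknown.

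**The error rates belong to a test that the plan does not name.** Also correct. The 10% figure is not a property of the Wilcoxon test, which as written tests for any difference rather than against the margin. The sample size reproduces on its own inputs and is not in question.

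**A 1 mg bias may be generous.** At r = 0.3 it needs a 0.64 SD imbalance in one covariate, which is 0.64/0.272 = 2.4 chance standard deviations, with two-sided probability about 0.02. Chance alone would rarely produce it. It takes a systematic difference, a stronger covariate or several smaller ones together. These are possible in a non-randomised comparison but not documented.

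**Surgeon and pain score are doubtful covariates.** The protocol says the three surgeons use the same operative technique. That does not settle differences in perioperative prescribing, but it weakens the case for spending 2 df on surgeon. Preoperative NRS is recorded differently in the two cohorts, and adjusting for such a measure can itself add bias. Both objections stand, and the fix keeps these two out of the primary model.

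**Conclusion.** The concern holds in this form: the primary comparison is neither randomised nor concurrent, only crude tests are planned, and nothing says which eligible TEA patients become the 30 controls. Any imbalance in measured patient characteristics would pass uncorrected into the primary result.

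The size is conditional. With an assumed net bias of 1 mg (0.19 SD), false non-inferiority goes from 2.5% to about 10%, or power from 0.79 to 0.55. This assumes a 4 mg margin, SD 5.2, 27 per group and a one-sided 0.025 test of means. The defect does not depend on those figures; its consequence does. The adjusted rates in the simulation are a best case, because the only confounder was measured and correctly modelled.

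This should be fixed, and it needs no redesign. The difference in the multimodal requirement is a difference in co-treatment to report, not case mix to adjust away; the two passages should be reconciled or the difference acknowledged.

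**What to change.** 1. **Control selection.** Take the 30 controls as consecutive eligible cases working back from the first prospective enrolment.

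2. **Primary analysis.** Prespecify a linear model of 48-hour opioid consumption on cohort, adjusted for a short fixed set available in both cohorts. One workable set is age, BMI, ASA class (III versus I-II) and preoperative daily opioid amount (4 df). Compare the upper 95% confidence limit for the cohort difference with the margin, and state whether that is 4 mg or 20% of the TEA mean. The exact set matters less than fixing it in advance.

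3. **Sensitivity analyses.** Keep the crude Wilcoxon. Add robust standard errors, and models adding surgeon or preoperative NRS, the latter only if the rest score is comparable in both cohorts.

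4. **Reporting.** Give a baseline table with standardised differences as description only: with a chance SD of 0.272, about 46% would exceed 0.2 by chance. Tabulate receipt of the multimodal regimen by cohort. State how many historical covariate values are missing and how they are handled. State that calendar period, which coincides with cohort, and unmeasured confounding cannot be adjusted for.

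**Cost.** Analysis wording, and chart extraction from records that the protocol already opens but describes as used where available. In power at 27/27, four covariate df cost about 0.04 if the covariates explain nothing (0.79 to about 0.75), more under real imbalance (about 0.72 in the case shown), and gain about 0.06 if they explain 20% of the variance. Adjustment removes only confounding that is measured and correctly modelled.
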